6.3 EXPLORATORY OBJECTIVE

An additional exploratory objective will be to evaluate primary and secondary objectives in at least 4 specific subgroups: treatment naïve patients, patients previously treated with a MS DMT within the past 2 years, injectable switch patients and oral switch patients.

7 STUDY DESIGN

7.1 DESCRIPTION OF THE STUDY DESIGN

This is a 2 year prospective, multicentre observational UK Study to describe HRQoL and other PROs in RRMS patients treated with Aubagio® (teriflunomide) 14 mg in a routine clinical practice. The study will be conducted at approximately 20 sites in the UK and will collect data on the current status, characteristics, and management of patients who are starting treatment with Aubagio® as part of their routine medical care.

The decision to treat with Aubagio® must be made prior to and independently from the proposal to enrol the patient on this study. All patients must be prescribed Aubagio® in accordance with the UK SmPC.

This is an observational study with no experimental intervention. Enrolled patients will receive treatment and evaluations for their MS as determined by their treating physicians in accordance with the local standard of care. Visits will be scheduled by the treating HCP according to patient-specific needs and local clinical practice. Administration of Aubagio® and monitoring of patients according to the SmPC and safety reporting will be the sole responsibility of the treating neurologist. Patients will be followed with laboratory monitoring in a regular healthcare setting in line with locally approved label requirements and the Risk Management Plan (RMP) for Aubagio®.

For purposes of this study, 6 visits are expected: study baseline (Visit 1), with follow up visits at months 3 (if part of clinical setting), 6, 12, 18 and 24. Patients will be expected to complete up to 7 questionnaires (see section 2.2) at different time points. Completing all of the questionnaires takes approximately 45 minutes. Questionnaires will be completed by the patient at the site during study visits or within 7 days before study visits (for visits V3-V6). Each questionnaire can be completed on a different day. However, a patient must complete an individual questionnaire in the same session once it has been started. Note: if a designated caregiver is available to assist the patient, they may physically complete the questionnaire for the patient. A nurse or other health care professional may assist with instructing the patient on how to complete a questionnaire.

Patient-reported outcomes, clinical outcomes and safety findings during routine clinical practice will be recorded for the entire cohort as well as for defined subgroups (i.e., patients who are treatment naïve, patients who switched from other DMT's). No control group will be included.

7.2 DURATION OF STUDY PARTICIPATION FOR EACH PATIENT

The duration of the study for each patient will be 2 years (24±1 months). There will be a maximum of 6 study visits for participating patients. Data collection will be at baseline (Visit 1) and at month 3* (Visit 2), month 6 (visit 3), month 12 (visit 4), month 18* (visit 5), and month 24/End of study (EOS).

The baseline visit should occur within 4 weeks of the first dose of Aubagio[®]. All other visits should occur within a time window of ±1 month.

Note that not all study sites will have a month 3 and / or month 18 office visit, according to local practice, but if a month 3 and/ or month 18 visit is performed, data will be collected). Additional visits may occur according to the local clinical practice.

Eligible patients who meet the inclusion and exclusion criteria and sign the informed consent will be enrolled into the study.

7.3 STUDY VARIABLES

28032018 Version number: Final 2.0

7.3.1 Baseline Visit

The following patient characteristics will be recorded at the baseline visit (completed within 4 weeks of first dose of Aubagio®):

- Patient demographics (gender, year of birth, smoking history)
- MS disease history
 - Date of first symptoms: month and year
 - Date of diagnosis: month and year
 - Number of relapses in the 2 years prior to enrolment
 - Time since last relapse
 - Disability progression/Expanded Disability Status Scale (EDSS) score
- Previous/current treatment with DMTs, if applicable
 - Treatment start and stop dates
 - Reason for starting/changing treatment
- Prior and concomitant medications
- Medical/surgical history and co-morbidities
- PROs (collected within 4 weeks of first dose of Aubagio®):
 - Multiple Sclerosis Impact Scale (MSIS-29) questionnaire
 - Modified Fatique Impact Scale (MFIS-5) questionnaire
 - Hospital Anxiety and Depression (HADS) guestionnaire
 - Symbol Digit Modalities Test
 - Multiple Sclerosis Intimacy and Sexuality (MSISQ-19) Questionnaire
 - Treatment Satisfaction Questionnaire for Medication version 1.4 (TSQM v1.4) questionnaire
 - Patient Determined Disease Steps (PDDS) questionnaire
- Number of scheduled and unscheduled HCP encounters within the past 12 months
- Number of emergency visits in past 12 months
- Health Related Productivity Question-MS (HRPQ-MS) questionnaire
- AEs/SAEs/AESIs since first dose of Aubagio® will be retrospectively collected upon signature of Informed Consent Form

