	 Adult patients (>18 years old) with RRMS according to a neurologist's diagnosis, where the physician and patient have decided to start treatment with Aubagio® according to the SmPC. 			
	2. Initiated Aubagio® treatment for the first time within 4 weeks of study entry			
	Patient having signed written informed consent			
	4. Patients who are willing and able to fill out the questionnaires for the full duration of the study.			
	Note: If a designated caregiver is available to assist the patient, they may physically complete the questionnaire for the patient. A nurse or other health care professional may assist with instructing the patient on how to complete a questionnaire.			
	Exclusion criteria:			
	 Patients with contraindications to Aubagio® according to SmPC Patients who are currently participating in an investigational interventional study if, in the judgment of the Investigator, such participation would interfere with the current study. Patients who are unwilling or unable to complete any questionnaire to be used in the study Women of child bearing age who are not willing to use an effective form of contraception 			
RECRUITMENT MODALITIES	Selection of Investigator			
	Investigators who are experienced in the treatment of patients with RRMS will undergo a feasibility assessment performed by Sponsor representatives. Selection of patients			
	Consecutive recruitment after decision to begin Aubagio® therapy, and determination of patient eligibility and willingness to participate. The decision to treat with Aubagio® must be made before considering a patient's entry into the study.			

Version number: Final 2.0

FNDPOINTS

Primary Endpoint

Mean change in Multiple Sclerosis Impact Scale (MSIS-29) scores from baseline to month 24.

Secondary endpoints

Clinical outcomes:

- Number of relapses (since baseline) at each visit and at month 24 Patient reported outcomes:
 - Disability accumulation: change in Patient Determined Disease Steps (PDDS) over time at each visit (except visit 2) and at month 24 compared with baseline
 - Fatigue: change in Fatigue score, assessed using the MFIS-5, at each visit (except visit 2) and at month 24 compared with baseline
 - Anxiety and Depression: Change in anxiety and depression at each visit (except visit 2) and at month 24 compared with baseline, as measured by the Hospital Anxiety and Depression Scale (HADS)

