Safety (AEs/SAEs/AESIs) since first dose of Aubagio will be retrospectively collected upon signature of the Informed Consent Form.

Visit 2 (Month 3) – only performed if part of routine clinical care.

- Prior and concomitant medications
- Number of relapses since last visit
- Treatment adherence number of missed doses since last visit
- Number of scheduled and unscheduled HCP encounters since last visit
- Number of emergency visits since last visit
- Safety information (AEs/AESIs/SAEs).

V3, V4, V5* V6/EOS

- Prior and concomitant medications
- Number of relapses since last visit
- MSIS-29
- MFIS-5
- HADS
- SDMT

- MSISO-19
- TSQM v1.4
- PDDS
- Treatment adherence Number of missed doses since last visit
- Number of scheduled and unscheduled HCP encounters since last visit
- Number of emergency visits since last visit
- HRPQ-MS (months 12 and 24/EOS only)
- Safety information (AEs/AESIs/SAEs)
- * Visit 5 only performed if part of routine clinical practice

Safety

- AEs/AESIs/SAEs since first dose of Aubagio® will be retrospectively collected upon signing Informed Consent Form.
- AEs/AESIs/SAEs will be recorded at each visit according to standard clinical practice
- Up to 3 Monthly telephone calls may be performed as and when needed in order to follow up on potential AEs/AESIs/SAEs.
- Patients will be followed with laboratory monitoring in a regular healthcare setting in line with local approved label requirements and the RMP for Aubagio[®].

STATISTICAL METHODOLOGY

The following represents an overview of planned analyses. Further elaboration of statistical issues will be specified in the Statistical Analysis Plan (SAP).

Sample size determination

The sample size has been calculated in order to assess the primary objective, describe changes in MSIS-29 scores from baseline to month 24. Mean MSIS-29 score on baseline, 24 months and changes during the follow-up (baseline to 24 months) will be calculated with the 95% confidence interval (CI). Taking into account a standard deviation of 20 points in MSIS-29 (Glenn, 2016), a sample size of 100 allows to estimate the MSIS-29 scores with a precision (distance from the mean to the limits of the 95% CI) of about 4 points with a significance level of 0.05. The sample size of 100 patients has been also determined based on the average number of patients at each site within the recruitment period of 2 years.

Analysis populations

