8.2 INCLUSION CRITERIA

- I 01. Adult patients (≥18 years old) with RRMS according to a neurologist's diagnosis, where the physician together with the patient have decided to start treatment with Aubagio® according to the approved SmPC.
- I 02. Initiated Aubagio® treatment for the first time within 4 weeks of study entry
- 103. Patients who have signed written informed consent
- 104. Patients who are willing and able to complete the questionnaires for the full duration of the study

Note: (if a designated caregiver is available to assist the patient, they may physically complete the questionnaire for the patient)

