11.3.2 Patient/Subject Tracking Logs

All consecutive patients who have started on Aubagio® in the past 4 weeks will be approached to enter the study. The patient's visit sequence will be documented in a patient tracking log for all enrolled and non-enrolled patients, with the reason for non-inclusion (not eligible or no consent). Data collected for patients who end up not enrolling are fully anonymous (gender, age).

The patient identification log for enrolled patients shall be kept by the Investigator to comply with the data privacy requirement. This log is not part of the eCRF and will not be entered into the clinical database.

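### Up to 28 days on Aubagio fall inside the baseline look-backs for relapses and healthcare use and outside the follow-up counts, and missed doses in those days are never recorded

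*Protocol*

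**What the plan says.** **Entry follows the first dose.** Section 8.2 requires "Initiated Aubagio® treatment for the first time within 4 weeks of study entry". Section 11.3.2 settles the order of events: "All consecutive patients who have started on Aubagio® in the past 4 weeks will be approached to enter the study". Section 7.2 adds: "The baseline visit should occur within 4 weeks of the first dose of Aubagio".

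**The look-backs end at entry or baseline.** Section 7.3.1 lists "Number of relapses in the 2 years prior to enrolment", "Number of scheduled and unscheduled HCP encounters within the past 12 months" and "Number of emergency visits in past 12 months". Footnote f of the flow chart in section 2.2 confirms the 12-month span for the two healthcare items. Only the relapse item names enrolment. The healthcare items run back from the baseline visit, which has the same effect.

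**Follow-up starts at baseline.** The synopsis endpoint is "Number of relapses (since baseline) at each visit and at month 24". Sections 7.3.2 and 7.3.3 collect relapses, encounters, emergency visits and missed doses for the interval from the previous visit. The flow chart has no missed-dose entry at Visit 1.

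**Adverse events are treated differently.** The synopsis says "Safety (AEs/SAEs/AESIs) since first dose of Aubagio will be retrospectively collected upon signature of the Informed Consent Form", and section 7.3.1 and flow-chart footnote e agree. The opening of section 13 and section 13.1.3, however, start collection at the first intake or dose that follows consent.

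**The concern.** The interval from first dose to baseline is time on drug, yet for relapses and healthcare use the protocol places it with the history. Take a patient who is enrolled on day 25 and had an emergency visit on day 10. That visit goes into the 12-month baseline count and is absent from every follow-up count. A dose missed on day 10 is recorded nowhere.

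The Visit 1 sections recognise this interval for adverse events and reach back to cover it. They do not do so for the other outcomes, so safety and the remaining secondary outcomes may be described over different exposure periods in the same patient.

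Relapses, healthcare encounters, emergency visits and missed doses are all named secondary endpoints. The difficulty lies in what is collected, so for the undated items a later analysis plan cannot repair it.

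**Working it through.** The protocol gives no figure on this point. Its one computed figure, the MSIS-29 precision, reproduces (1.96 × 20/√100 = 3.92, about 4 points) but plays no part here.

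**Inputs from the protocol**
- Gap g between first dose and baseline: 0 to 4 weeks, so at most 28 days (7.2, 8.2, 11.3.2).
- Relapse look-back: 2 years = 730.5 days. Healthcare look-back: 12 months = 365.25 days (7.3.1).
- Follow-up: 24 months from baseline (7.2).

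**Share of each window affected**

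| Gap | g/730.5 (relapse look-back) | g/365.25 (healthcare look-back) | g/(730.5 + g) (on-drug time to month 24) |
|---|---|---|---|
| 7 days | 1.0% | 1.9% | 0.9% |
| 14 days | 1.9% | 3.8% | 1.9% |
| 28 days | 3.8% | 7.7% | 3.7% |

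If month 24 is counted from the first dose instead, the last figure is 28/730.5 = 3.8%.

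**Adherence.** Over 24 months the uncollected share is again at most 28/758.5 = 3.7%. It is larger at early visits: 28/(182 + 28) = 13% at Visit 3 if Visit 2 is not held, and 28/(91 + 28) = 24% at Visit 2. That last figure needs the full gap and a visit that is optional.

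**Direction for relapses (assumed rates; the protocol gives none).** Let the annual rate be a = 0.6 before the drug, e in the first 4 weeks and b = 0.3 afterwards, with w = 4/52.18 = 0.0767 years.
- As written: history rate = [(2 − w)a + we]/2; follow-up rate = b.
- Split at first dose: history rate = a; follow-up rate = [we + (2 − w)b]/2.

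| e | Ratio as written | Ratio split at first dose | Relapses in the gap per 100 patients (100we) |
|---|---|---|---|
| 0.3 | 0.300/0.5885 = 0.51 | 0.300/0.600 = 0.50 | 2.3 |
| 0.6 | 0.300/0.600 = 0.50 | 0.3115/0.600 = 0.52 | 4.6 |
| 1.2 | 0.300/0.623 = 0.48 | 0.3345/0.600 = 0.56 | 9.2 |

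The sign changes. With a low early rate the wording makes the before/after contrast slightly less favourable to the drug. With a high early rate it makes it more favourable.

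**Healthcare encounters (assumed).** With r encounters a year before treatment and k in the first 4 weeks, the 12-month baseline count as written is r(1 − w) + k, against r before the first dose.
- r = 8, k = 1: 8.39, or +5%.
- r = 4, k = 3: 6.69, or +67%.
- k = 0: the count falls by 7.7% for any r.

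**What can be recovered**
- *Relapses:* section 7.3.1 records the time since the last relapse. The first-dose date is needed for eligibility. A relapse in the gap is the most recent one at Visit 1, so the two values identify it, unless two relapses fall within 28 days. The time must be recorded finely enough; the protocol gives no unit.
- *Encounters and emergency visits:* listed as counts without dates, so they cannot be split.
- *Missed doses before baseline:* not collected.

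**The case against.** The protocol never calls these windows pre-treatment. Its relapse objective concerns the two-year study period, and counting from study baseline fits that objective. The windows adjoin without gap or overlap. Relapses, encounters and emergency visits are listed as numbers, not changes. Section 14.3.1.2 applies the same methods as for the questionnaire scores, but does not say that a 2-year or 12-month history is the comparator. All this stands, so a before/after contrast of these counts is a possible use and not a stated one.

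A reader might go further and infer that the wording flatters the drug by moving early events from after to before. The documents do not support that. A look-back of fixed length that gains four on-drug weeks also loses four weeks at its far end, so the net effect depends on early event rates that the protocol does not give. For missed doses the data are simply absent and show no direction.

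A reader might also take the 24% adherence figure as the size of the problem. It is a maximum at an optional visit. Nor can adverse events be held up as a settled contrast, since section 13 conflicts with the Visit 1 sections on where their collection starts.

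The objection does not remove the loss of information. On the items listed, nobody can later separate on-drug healthcare use from earlier use, or reconstruct early adherence.

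**Conclusion.** The point holds in limited form. Up to 28 on-drug days per patient sit in the baseline look-backs (at most 3.8% for relapses and 7.7% for healthcare use) and are missing from follow-up (at most about 3.7% of on-drug time to month 24). Missed doses in that interval are not recorded. These are ceilings, and a shorter gap scales them down. The direction of bias is unknown.

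The relapse part is small and largely recoverable. The healthcare and adherence parts are not recoverable from the items listed, and the healthcare effect could be larger than its share of time if contacts cluster around the start of treatment, which is an assumption. The primary endpoint's change score does not use these counts. This is a modest correction to several secondary endpoints of an uncontrolled, descriptive study, worth making because it is cheap and cannot be made at analysis.

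**What to change.** In the synopsis, section 2.2 and section 7.3.1, end the relapse, encounter and emergency-visit look-backs at the date of first dose. At Visit 1, record separately the relapses, encounters, emergency visits and missed doses between first dose and baseline, so that they can be reported as on-treatment. Make the synopsis and section 7.4.2 agree on the origin of the relapse count.

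Reconcile the start of adverse-event collection in section 13 and section 13.1.3 with the synopsis, flow-chart footnote e and section 7.3.1.

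The cost is a protocol and eCRF amendment, which section 18 notes may need regulatory submission, and four short retrospective items over an interval that the Visit 1 sections already have sites review for adverse events. Any patients already enrolled would have differently defined windows, and the report would need to say so.

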7.3.2 Visit 2 (Month 3)

The following data will be recorded at visit 2 (month 3), this visit will only occur if part of routine clinical practice:

- Prior and concomitant medications
- Number of relapses since last visit
- Treatment adherence number of missed doses since last visit
- Number of unscheduled and scheduled HCP encounters since last visit
- Number of emergency visits since last visit
- Safety information (AEs/AESIs/SAEs)

7.3.3 Visits 3, 4, 5 and 6/EOS

The following data will be recorded after initiation of Aubagio® (V3, V4, V5, V6/EOS). Visit 5 will only occur if part of routine clinical practice:

- Prior and concomitant medications
- Number of relapses since last visit
- PROs:
 - MSIS-29 questionnaire
 - MFIS-5 questionnaire
 - HADS questionnaire
 - SDMT
 - MSISQ-19 questionnaire
 - TSQM v1.4 questionnaire
 - PDDS questionnaire
- Treatment adherence number of missed doses since last visit
- Number of unscheduled and scheduled HCP encounters since last visit
- Number of emergency visits since last visit
- Safety information (AEs/AESIs/SAEs)

In addition to the study visits there may be up to 3 monthly telephone calls between the study visits from the sites to the patients as and when needed in order to follow up on potential AEs/AESIs/SAEs. The results of these calls will also be documented in the study CRF.

Patients will be followed with laboratory monitoring in a regular healthcare setting in line with local approved label requirements and the Risk Management Plan (RMP) for Aubagio[®].

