5.2 RATIONALE

Aubagio® (teriflunomide; A771726, ATC code L04AA31) is a once-daily, oral disease-modifying therapy (DMT) indicated for the treatment of patients with relapsing remitting MS (RRMS). Aubagio® has shown significant efficacy across a number of key measures for MS disease, including relapse rate reduction, slowing the progression of physical disability and reducing the number of brain lesions as detected by magnetic resonance imaging (MRI) [13-15]. The cumulative exposure to Aubagio® in the clinical program exceeds 6800 patient-years, and in long-term studies individual exposure exceeds 12 years [16]. Aubagio® once-daily 14 mg oral tablets were approved in June 2014 for the treatment of adult patients with RRMS to reduce the frequency of clinical relapses and to delay the progression of physical disability.

The functional consequences of MS disease progression, such as increased fatigue, changes in cognition, increased disability and reduced ability to work are important from the patients' perspective as well as the clinician's and impact overall quality of life [17-20].

Over the past several years, the development of evaluations for PROs has provided the tools to assess patient outcomes in clinical practice and real world settings. Various instruments to collect patient reported outcomes have been developed and validated in MS and provide a means by which patients can document important information on their disease state and the impact of MS treatment on their overall quality of life.

Health authorities (e.g. EMA) encourage the use of quality of life assessment in patients with chronic illness [9], and several groups have published detailed recommendations for HRQoL assessments in the evaluation and approval for medicinal products [10, 11].

Property of the Sanofi group - strictly confidential

TERIFL08182 - teriflunomide

Version number: Final 2.0

Despite the acknowledged need to consider HRQoL, in routine clinical practice these assessments remain underutilized [12]. Recognising this gap and considering the main neuropsychiatric features of MS, the objective of this observational study is to provide real world patient reported outcomes in MS patients treated with Aubagio®. This study will assess PROs measuring HRQoL, treatment adherence and satisfaction, and health economics outcomes in real-life medical practice in patients with RRMS.

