7.4.4.9 Health Related Productivity Questionnaire-MS Version 2 (HRPQ-MS) v2

The HRPQ-MS v2 is a comprehensive instrument that measures several aspects of health-related lost productivity, such as absenteeism and attendance for paid and unpaid work, and long-term loss of workforce participation. It was designed for patients who have a particular disease and/or are being treated for the disease. The HRPQ-MS v2 consists of 9 questions that can be divided into 4 sections:

- Patient's employment status (full-time, part-time, not currently employed)
- Number of hours missed due to the disease/treatment, and percent of impact of the disease/treatment on work output (patients employed full- or part-time)
- Impact of the disease/treatment on productivity related to household chores (patients not currently employed)
- Disease history, including whether the disease/treatment forced the patient to change working situation (e.g., go from full-time to part-time, quit working, etc.).

The HRPQ-MS v2 asks patients to report lost productivity in the past week to minimize recall bias. Administration time is approximately 5 minutes at baseline collection and 3 to 4 minutes at follow-up.

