14.3.1.2 Secondary Analysis

The changes from baseline to month 24, and to each follow-up visit before 24 months visit, in TSQM v1.4, PDDS, MFIS-5, HRPQ-MS v2, MSISQ-19, SDMT and HADS will be tested using the t-distribution. The mean changes between study visits with the corresponding 95% confidence interval will be given. If required, an ANCOVA, adjusting for baseline covariates will be performed. A p-value below 0.05 will be considered statistically significant. The evolution of PRO scores during the follow-up period will be also represented graphically.

In addition to PRO scores, the same statistical methods will be used to analyse number of missed doses of Aubagio® (adherence), number of relapses, number of HCP encounters and number of emergency room visits.

Additional exploratory pre-specified analysis of the secondary endpoints will be performed in at least 4 specific subgroups: treatment naïve patients, patients previously treated with a MS DMT within the past 2 years, injectable switch patients and oral switch patients.

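### Missed doses are counted over a look-back of 3, 6 or 12 months depending on visit and site, with no denominator, so a trend in adherence cannot be interpreted

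*Protocol*

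**What the plan says.** Adherence is a secondary objective (Protocol 6.2). Its endpoint in 7.4.2 is simply the number of missed doses, listed among the patient reported outcomes, with no rate or percentage. At every follow-up visit the item collected is "Treatment adherence number of missed doses since last visit" (7.3.2, 7.3.3 and the flow chart in 2.2). There is no adherence entry at baseline. The drug "is a once-daily, oral disease-modifying therapy (DMT" (5.2), so there is one dose to miss per day.

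The schedule in 7.2 is baseline, then "month 3* (Visit 2), month 6 (visit 3), month 12 (visit 4), month 18* (visit 5), and month 24/End of study (EOS". The starred visits are optional: "Note that not all study sites will have a month 3 and / or month 18 office visit, according to local practice". On timing, "All other visits should occur within a time window of ±1 month", and "Additional visits may occur according to the local clinical practice". The protocol does not say whether an additional visit counts as the last visit for this item. Under 8.5, a patient who stops treatment early has the end-of-study evaluations brought forward, so the last interval then has no set length.

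For analysis, section 14.3.1.2 describes mean changes between visits, tested with the t-distribution, for the questionnaire scores and then states that "the same statistical methods will be used to analyse number of missed doses of Aubagio® (adherence"), along with relapses, encounters and emergency visits.

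For the productivity questionnaire, section 7.4.4.9 notes that it "asks patients to report lost productivity in the past week to minimize recall bias".

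**The concern.** A count is comparable between two visits only if both cover the same amount of time at risk and are obtained equally well. Here neither holds. The time covered depends on which visit it is and on whether the site routinely sees patients at months 3 and 18. If the number comes from the patient's memory, the quality of the answer also depends on how far back the question reaches.

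At stake is one secondary endpoint, but it is the study's only description of adherence over two years. A mean change in raw counts would largely track the calendar. A later analysis can divide by interval length, but it cannot restore doses that were forgotten when the question was asked. That is why the wording of the question, which the protocol fixes, matters more than the analysis method.

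**Working it through.** The protocol gives no figure for adherence, so there is none to reproduce.

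**Step 1: the look-back.** Nominal intervals in months, from the visit months in 7.2:

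| Optional visits held | Successive look-backs |
|---|---|
| Month 3 and month 18 | 3, 3, 6, 6, 6 |
| Month 3 only | 3, 3, 6, 12 |
| Month 18 only | 6, 6, 6, 6 |
| Neither | 6, 6, 12 |

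The span lengthens in three patterns and is constant in one. The month 6 report covers 3 or 6 months, and the month 24 report covers 6 or 12. With the ±1 month windows, month 12 to month 24 without a month 18 visit can reach 25 − 11 = 14 months.

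**Step 2: the endpoint as written (raw count).** Assume 5% of doses are missed throughout, and nothing is forgotten. With 30.4375 days per month, count = 0.05 × 30.4375 × months:

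- 3 months: 4.57
- 6 months: 9.13
- 12 months: 18.26

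The 5% is illustrative, but the ratio of 1 : 2 : 4 does not depend on it. Let a share a of patients have the month 3 visit and a share b the month 18 visit. The mean look-back is then 6 − 3a months at month 6 and 12 − 6b months at month 24, ignoring dropout. The ratio (12 − 6b)/(6 − 3a) runs from 1 (a = 0, b = 1) to 4 (a = 1, b = 0). It equals 2 whenever a = b. Under that condition the mean count doubles between month 6 and month 24 with unchanged behaviour.

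**Step 3: a rate, with imperfect recall.** The documents give no recall figure. Assume full recall of the last 3 months and a fraction r before that. For span w, the fraction reported is (3 + (w − 3)r)/w. Applied to a true 5%:

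| r | Rate, 3 months | Rate, 6 months | Rate, 12 months | Fall 3 to 6 | Fall 6 to 12 |
|---|---|---|---|---|---|
| 0.50 | 5.0% | 3.75% | 3.13% | 25% | 16.7% |
| 0.75 | 5.0% | 4.38% | 4.06% | 12.5% | 7.1% |
| 0.90 | 5.0% | 4.75% | 4.63% | 5% | 2.6% |

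**Step 4: the count under the same recall model.** At r = 0.50 the reported counts are 4.57, 9.13 × 0.75 = 6.85 and 18.26 × 0.625 = 11.41. The count still rises. This is general: if the chance of recalling a miss depends only on how long ago it happened, a longer interval can add to the count but not reduce it.

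**Step 5: a different recall curve.** If recall decays with a half-life of 3 months, the counts over 3, 6 and 12 months are 3.3, 4.9 and 6.2. The rates are 1.10, 0.82 and 0.51 missed doses per month against a true 1.52. The directions are the same: the count goes up and the rate goes down.

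**The case against.** A reader might infer that forgetting alone will make adherence appear to improve over two years, and might put the apparent fall in missed doses at 38% (5.0% to 3.13%). The documents do not support that reading.

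- The endpoint is a raw count, and the raw count moves the other way. Apparent improvement needs a conversion to a rate, which the protocol does not state, as well as recall decay, for which it gives no figure.
- A change from a 3-month to a 12-month span occurs within patients only where month 3 is held and month 18 is not. Where month 18 is held and month 3 is not, the span is a constant 6 months and neither artefact produces a trend.
- At 90% recall the fall in the rate is small.

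Other points for the plan also carry weight. Patient recall is inferred from the heading under which 7.4.2 lists adherence; it is not a stated procedure, and 11.2 counts hospital records among source data. The one-week period in 7.4.4.9 is a property of an existing questionnaire, not a judgement about missed tablets. It shows only that the protocol recognises recall length as a source of bias. The adherence endpoint lacks the per-visit wording given to the scales, no comparison between sites is planned, and a statistical analysis plan could add a denominator. Counting since the last visit also covers follow-up without gaps, which suits a total.

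These points limit the direction and size that can be claimed. They do not answer the main one: section 14.3.1.2 extends mean-change methods to counts taken over unequal spans, and a denominator added later would correct exposure but not recall.

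**Conclusion.** The point holds in this form: the look-back is not fixed, no denominator is stated, and the planned analysis treats the counts as if they were comparable.

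The exposure artefact follows from the schedule alone, given a constant miss rate. The count doubles from a 3-month to a 6-month span and doubles again to 12 months, so adherence appears to worsen where the interval lengthens. The recall artefact is conditional. It appears only if a rate is used and the answers rest on memory that fades, and its size over the assumed 50% to 90% recall is a fall of 25% to 5% (3 to 6 months) or about 17% to 3% (6 to 12 months).

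Because the two artefacts pull in opposite directions, neither the count nor the rate gives a trend, or a contrast between visit patterns, that can be read as behaviour. The primary endpoint is unaffected. The change should be made because it is cheap and cannot be fully made after data collection.

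**What to change.** In Protocol 2.2, 7.3.2, 7.3.3 and 7.4.2, ask for missed doses over one fixed short period before each visit, for example the past 4 weeks, identical at every visit and site. Define the adherence endpoint as the percentage of doses missed in that period, and amend 14.3.1.2 to match.

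Keep the since-last-visit item as supporting data. Report it as missed doses divided by doses due, together with the interval length, and do not analyse it as a mean change in raw counts. State whether an additional visit resets the interval.

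The cost is one added or reworded eCRF question per visit and a few lines of analysis wording. The drawback is coverage: a 4-week period at 3 to 5 follow-up visits samples 12 to 20 of about 104 weeks. The retained item covers the rest.
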